The proposed agent for the current study, Optison™ is a sterile non-pyrogenic suspension of encapsulated perflutren microbubbles [Goldberg et al 2001; Miller & Nanda 2004]. The contrast agent is consists of a human serum albumin shell with perflutren core and contains  $5.0 - 8.0 \times 10^8$  microspheres/ ml. The microbubble agent is supplied in a standard-size 3 ml vial and is prepared by manually shaking the vial. Optison will be stored in a secure refrigerator, with only the study investigators and research personnel having access. Optison is currently only approved for use in echocardiography. The agent will be used as an off-label indication for this study.

**Statistical Methodology:** This project is a pilot study to determine if CEUS can be used for the evaluation renal cell carcinoma recurrence post cryoablation.

Our statistical analysis will address two major questions:

1. Does renal mass vascularity and blood flow kinetics measured on CEUS correlate with findings on contrast-enhanced MRI/CT (and thus, can be used as a possible recurrence screening imaging alternative)?
2. Does the inclusion of volumetric ultrasound improve the sensitivity and specificity of CEUS for monitoring recurrence of RCC post cryotherapy?

Sensitivity, specificity, accuracy, positive predictive value, and negative predictive value will be calculated for the CEUS exams using both the standard of care contrast-enhanced MRI or CT, or pathology when retreatment is indicated as the reference standards. The dichotomous parameter needed for these calculations will be derived by ascertaining whether blinded radiologists would recommend repeated treatment or not based on the degree of residual blood flow observed during the CEUS study. This parameter will be based off of each reader's first read. In the event of discordant readings during this analysis, recurrence will be decided by consensus by the two readers. Correlations between these findings and both contrast-enhanced cross-sectional findings and patient outcomes will be compared using the Fisher exact test. Inter- and intra-observer variability will also be calculated. Quantitative parameters of mass vascularity, changes in perfusion, and changes in contrast fill time will also be

computed and again correlated to the clinical standard.

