#### 6.5 Efficacy Assessments

Both 2D and 3D CEUS exams and the clinically-indicated contrast-enhanced MRI/CT exam will be independent and randomly reviewed by two blinded radiologists with experience in both CEUS and body imaging. Readers will evaluate the presence of signal enhancement within the mass, signal distribution and heterogeneity, signal intensity relative to the normal renal parenchyma, and contrast agent wash-in and wash-out kinetics relative to the surrounding parenchyma. The readers will also be asked to evaluate if CEUS findings indicate RCC recurrence. Recurrence will initially be defined as the presence of contrast enhancement within the ablation cavity. Finally, following a one month wait period and randomization, readers will again review cases in order to calculate intra-reader variability. Both qualitative and quantitative findings will be obtained for the ultrasound study. Sensitivity, specificity,

accuracy, positive predictive value, and negative predictive value will be calculated for the contrast-enhanced ultrasound exam using both the standard of care contrast-enhanced CT or MRI, and pathology (if retreated) as the reference standards. The dichotomous parameter needed for these calculations will be derived by ascertaining whether blinded radiologists would recommend further treatment or not based on the degree of residual blood flow observed during the CEUS study. Correlations between these assessments and both contrast-enhanced MRI or CT findings will be compared using the Fisher exact test. Inter- and intra-observer variability will also be calculated. Quantitative parameters of mass vascularity, perfusion, and contrast fill time will be computed relative to the surrounding renal parenchyma and again correlated to the clinical standard. Finally, the patient's billed amount for their contrast-enhanced MRI/CT exam (cost of exam prior to insurance reimbursements) will be recorded and compared to the cost of a real ultrasound exam and one vial of ultrasound contrast agent to compare potential cost savings to the patient. Quantitative parameters will be compared between recurrent and disease free groups using a Student's t-test.

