Data will first be analyzed on a per case basis (treating each case as an independent data point). However, analysis may also be performed on a patient by patient basis if a large number of enrolled patients undergo serial imaging (potentially required to ensure adequate enrollment). Sensitivity, specificity, accuracy, positive predictive value, and negative predictive value will be calculated for the qualitative data using both the standard of care contrast-enhanced CT or MRI, and pathology (if retreated) as the reference standard. The dichotomous parameter needed for these calculations will be derived by ascertaining whether blinded radiologists would recommend further treatment or not based on the degree of residual blood flow observed during the contrast-enhanced ultrasound. Correlations between these findings and both contrast-enhanced MRI or CT findings will be compared using the Fisher exact test. Inter-rater variability will be calculated using each reader's first set of reads, while intra-rater variability will be calculated by comparing each reader's initial and 1 month analysis. Intra-rater and inter-rater variability will be calculated using a Shrout and Fleiss Interclass Correlation [Shrout and Fleiss 1979]. Quantitative parameters will be compared between groups using a Student's t-test.

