### 7.2.1 Sample Size Calculation

We hope to enroll up to 100 patients within 22 months as part of this study. This should be achievable,

given that our Urology clinic sees approximately 200 cryoablation follow up patients annually. As this is a pilot feasibility study it is difficult to estimate statistical power *a priori*. However, a power analysis was run in PASS12 (NCSS LLC, Kaysville, UT) to estimate the size of the confidence interval when estimating the test's overall level of specificity. A two sided confidence interval of one proportion was simulated using a Clopper-Pearson exact solution, assuming 100 patients and a total study recurrence rate of 5%. The relationship between the confidence level and 95% confidence interval and confidence interval width is shown below.

Confidence Level	Size (N)	Target Width	Actual Width	Proportion (P)	Lower Limit	Upper Limit	Width if P = 0.5
0.800	95		0.089	0.900	0.849	0.938	0.141
0.850	95		0.099	0.900	0.842	0.941	0.157
0.900	95		0.112	0.900	0.834	0.946	0.177
0.950	95		0.131	0.900	0.821	0.952	0.209

Thus, we expect 100 patients will enable us to estimate the specificity of the test to within 11% with 90% confidence. While multiple time points of the same patients cannot strictly be treated as independent samples (required to achieve adequate sample size within the two year window), data will also be analyzed on a per patient basis. Additionally, data from this study will also be used for future grant submissions to run a fully powered study in which conclusive hypotheses comparing 2D and 3D, as well as quantifiable parameters can be answered.

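### No discrimination measure is planned for the quantitative CEUS parameters: a t-test of group means does not show how well a parameter identifies recurrence in an individual exam

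*Combined protocol and SAP*

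**What the plan says.** **Quantitative parameters.** Section 7.2 derives mass vascularity, perfusion and contrast fill time from fitted wash-in and wash-out curves. Two analyses are planned for them:

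- A test of means. Section 6.5: "Quantitative parameters will be compared between recurrent and disease free groups using a Student's t-test". Section 7.2: "Quantitative parameters will be compared between groups using a Student's t-test". Neither section gives a significance level or sidedness.
- A correlation. Section 6.5 says the parameters "will be computed relative to the surrounding renal parenchyma and again correlated to the clinical standard". No coefficient or method is named.

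No cut-off, ROC curve, AUC or sensitivity at a fixed specificity is planned for any of them.

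**Reader-based result.** The accuracy measures belong to this result. Section 7.2 says that "accuracy, positive predictive value, and negative predictive value will be calculated for the qualitative data", and that the yes/no test result is "derived by ascertaining whether blinded radiologists would recommend further treatment or not". It is a reader's judgement, not a threshold on a measured parameter.

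**Purpose.** The first of the two statistical questions in the Synopsis is: "Does renal mass vascularity and blood flow kinetics measured on CEUS correlate with findings on contrast-enhanced MRI/CT (and thus, can be used" as a possible alternative for recurrence screening).

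**Size.** Section 7.2.1 plans the study "assuming 100 patients and a total study recurrence rate of 5" per cent, in order "to estimate the size of the confidence interval when estimating the test's overall level of specificity". The table uses N = 95 and a specificity of 0.900.

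**The concern.** A screening parameter is useful if its value in one exam separates recurrence from no recurrence. A t-test asks only whether the two group averages differ. They can differ clearly while most individual values overlap, and the planned output would not show this. The unnamed correlation does not fill the gap, because a correlation coefficient gives neither sensitivity nor specificity.

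Two things are at stake. First, a p-value below 0.05 for, say, fill time could be cited in favour of quantitative CEUS screening when the parameter would miss many recurrences at an acceptable false-positive rate. Second, Section 7.2.1 says the data will feed grant applications for a fully powered study that addresses the quantifiable parameters. That study needs an estimate of discrimination and of its uncertainty for each parameter, and a p-value for a difference in means supplies neither.

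**Working it through.** **Inputs from the plan (Section 7.2.1).** 100 patients and 5% recurrence give 5 recurrent and 95 disease-free. The planning specificity is 0.900.

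**Assumptions not in the plan.** Two-sided 0.05, normal data, equal SDs, one independent exam per patient, and the observed difference taken as the true one.

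**1. The plan's own figure.** Clopper-Pearson limits with N = 95 and x = 0.9 × 95 = 85.5 are:

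| Confidence | Lower | Upper | Width |
|---|---|---|---|
| 80% | 0.849 | 0.938 | 0.089 |
| 85% | 0.842 | 0.941 | 0.099 |
| 90% | 0.834 | 0.946 | 0.112 |
| 95% | 0.821 | 0.952 | 0.131 |

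All four rows match the table, so 5 v 95 and 90% specificity are the right planning values to use.

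**2. Smallest significant standardised difference.** d = t(0.975, 98 df) × √(1/5 + 1/95) = 1.984 × 0.4588 = 0.911.

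**3. What that difference means for discrimination.**

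- AUC = Φ(d/√2) = Φ(0.644) = 0.740.
- Sensitivity at 90% specificity = Φ(d − 1.282) = Φ(−0.371) = 0.355.

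**4. Range, one assumption varied at a time.**

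| Change from the base case | Sensitivity at 90% specificity |
|---|---|
| Base: 5 v 95, two-sided 0.05, equal SDs | 36% |
| Split 2 v 98 | 55% |
| Split 3 v 97 | 45% |
| Split 8 v 92 | 29% |
| Split 10 v 90 | 27% |
| One-sided 0.05 | 30% |
| SD in recurrent exams 0.5 × that in disease-free | 22% |
| SD in recurrent exams 2 × | 44% |
| SD in recurrent exams 3 × | 47% |

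**5. Larger true differences at 5 v 95, two-sided 0.05.** At d = 1.29 the t-test has about 80% power, and sensitivity at 90% specificity is Φ(1.29 − 1.282) = 50%. To reach 90% sensitivity at 90% specificity, d must be 2 × 1.282 = 2.56.

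**6. Does a non-significant result hide a good parameter?** Power of the same t-test by true AUC is:

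| True AUC | Power |
|---|---|
| 0.74 | 50% |
| 0.80 | 73% |
| 0.85 | 89% |
| 0.90 | 97% |
| 0.95 | 99.9% |

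It rarely does. Modest separation is often missed, strong separation seldom.

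**7. Precision of what would be reported instead.** The Hanley-McNeil SE for AUC 0.74 at 5 v 95 is 0.130, so the 95% interval is 0.74 ± 1.96 × 0.130, about 0.49 to 1.00. With 5 recurrences sensitivity moves in steps of 20 percentage points, and 2 of 5 has an exact 95% interval of 5% to 85%.

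**The case against.** The strongest defence is that diagnostic accuracy is already the main analysis. Sensitivity, specificity, accuracy and both predictive values are planned for CEUS against CT/MRI and pathology, from blinded readers who themselves assess enhancement and wash-in/wash-out kinetics. The protocol calls itself a pilot feasibility study, leaves conclusive hypotheses on quantifiable parameters to a later trial, and attaches no success rule to a t-test. Asking first whether a parameter differs between groups is conventional in a pilot. All of this stands, and it limits the point to a supporting analysis. It does not supply the missing measure: the reader result says nothing about how well a measured parameter discriminates.

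The 36% is also a boundary case. It takes the smallest significant difference as the truth, at a specificity that the plan sets for the test overall and not for any quantitative parameter. This also stands, so the figure is an illustration of what significance can mean and not a forecast.

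Three stronger readings are tempting, and the documents do not support them:

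- *The trial has the wrong estimand, or measures no diagnostic ability.* The reader-based analysis does measure it. Even d converts to an AUC under normality, although the plan makes no such conversion.
- *With 5 recurrences, non-significance would hide a parameter that separates well.* Step 6 shows 89% power at AUC 0.85 and 97% at 0.90.
- *The p-value conceals the imprecision.* At p = 0.05 the interval for the mean difference just touches zero, and the AUC interval of 0.49 to 1.00 just reaches 0.5. It is essentially the same fact on another scale.

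**Conclusion.** The point holds as a gap in a supporting analysis. Sections 6.5 and 7.2 give the quantitative parameters a test of means and an unspecified correlation, and neither shows how well a parameter identifies recurrence in one exam. Under two-sided 0.05, normality, equal SDs and 5 v 95, a just-significant result corresponds to AUC 0.74 and about 36% sensitivity at 90% specificity. Changing the split, SD ratio or sidedness one at a time gives about 22% to 55%, and larger differences imply better sensitivity. The reader-based accuracy analysis, which serves the primary objective, is unaffected. A reader should not infer that the trial cannot answer its diagnostic question, or that the t-test would usually miss a strong parameter.

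**What to change.** In Sections 6.5 and 7.2, for each quantitative parameter and each mode in which it is computed:

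1. Report the AUC for recurrent v disease-free with a 95% interval that allows for repeat exams in the same patient, for example a bootstrap that resamples patients. Section 7.2 otherwise treats each exam as independent, and Section 7.2.1 concedes that repeat exams are not strictly so.
2. Compare 2D with 3D by the paired AUC difference, with an interval obtained in the same way.
3. If sensitivity at 90% specificity is shown, give its exact interval and state that the cut was chosen on the same data.
4. Label all of this exploratory. The t-test, or group means and SDs, may stay as description.

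This needs no new patients, procedures or data, only plan wording and a little more analysis. The drawback is wide intervals with about 5 recurrences and an unstable sensitivity estimate, and the report should say so plainly.

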## 6.6 Safety Assessments

Adverse events will be monitored during the entire procedure. Specifically, the patient will be monitored with non-leading questions to monitor the patient for the transient side effects that are described below.

### 6.6.1 Risks/Benefits Assessment.

Serious cardiopulmonary and allergic reactions including fatalities have occurred during or following administration of Optison, causing the FDA to place a black box warning on the agent. However these occurrences have been rare (less than 1 in 5,000 patients). As a result, patients with cardiac shunts or unstable cardiopulmonary conditions will be excluded. All contrast injections will be supervised by a board certified physician. Resuscitation equipment and trained personnel will be immediate proximity to the patient during each contrast-enhanced ultrasound exam. Patients will also be monitored for 30 minutes after contrast administration for any adverse reactions. The majority of adverse events from Optison were transient and mild in severity. Of the reported adverse reactions following the use of Optison the most frequently reported were headache (5.4%), nausea and/or vomiting (4.3%), warm sensation or flushing (3.6%), and dizziness (2.5%).

The use of an intravenous needle and the fluids given through the needle may cause minor discomfort, bleeding under the skin (bruise), and possible infection at the site of needle insertion.

Clinically significant adverse effects from the administration of Optison are unlikely. The validation of an imaging technique which could replace a clinical standard that uses in a nephrotoxic contrast media in renally compromised patients would be of immense benefit.

To minimize and/or eliminate risks a nurse will be present during the entire procedure. Adverse events will be monitored during the entire procedure and for 30 minutes post injection.

The risk benefit ratio is low. Based on the available non-clinical and clinical safety data and the dosage levels of Optison that will be used in this study, safety concerns are minimal. The potential side effects related to Optison administration are described in Table 1 above.

#### 6.6.2 Adverse Events

An AE includes any condition that was not present prior to trial treatment, but appeared following initiation of trial medication; any condition that was present prior to trial treatment, but worsened during trial medication; or any condition, of which the subject has a history, that was not present prior to trial medication initiation but reappeared following administration of Optison. This would include conditions that are likely to be associated with an underlying or intermittent disease (e.g., angina, flu, etc.).

The subjects will be monitored for AEs during the entire procedure. All AEs, including both observed or volunteered problems, complaints, signs or symptoms, and diagnoses, occurring from the initiation of Optison dosing until the completion of the Optison administration will be recorded on a serious or non-serious AE data form, whether or not associated with the use of the trial medication. All adverse events are reported to the Clinical Trial Support Office (CTSO) via the password protected Kimmel Cancer Center Adverse Event Reporting System. In addition all unexpected and serious adverse events (SAEs) are reported to the TJU IRB and to the Food and Drug Administration (FDA) if applicable. The investigator is required to submit all unexpected and serious adverse events to the TJU IRB and the DSMB within 48 hours. Fatal adverse events related to treatment which are unexpected must be reported within 24 hours to the TJU IRB and the DSMB through the CTSO. Fatalities not related to the study drug/device must be reported within 5 days.

The AE forms will include: subject identification number and initials; subject's date of birth, gender, and ethnicity; date of Optison administration; signs/symptoms and severity; date of onset; date of resolution or death; relationship to the study drug; action taken; concomitant medication(s) including dose, and route and duration of treatment.

Whenever possible, the AE will be evaluated and reported as a diagnosis rather than individual signs and symptoms. If a definitive diagnosis is not possible, the individual signs and symptoms will be recorded. The investigator will evaluate and note the duration, intensity, and relationship to (association with) the Optison administration, the action taken, and the determination of seriousness for each AE.

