### 3.1 Trial Duration

Individual participation for the majority of patients will be limited to 1 ultrasound exam during their cryoablation follow up in Thomas Jefferson University's Urology clinic. However, patients will be eligible for serial imaging (for example exams at 8, 12 and 18 months), if these exams fit within the study timeframe. Exams will take place the day of the patient's MRI/CT follow up or during their Urology clinic follow up (in cases where MR/CT imaging is performed outside of Jefferson). The entire ultrasound imaging protocol will require approximately one hour including a 30 min observation period. Patients will be monitored for at least 30 minutes before being discharged.

Subject recruitment is expected to last 22 months (January 2015 – November, 2016). Analysis and publication of results are expected to take an additional 2 months (November 2016– January, 2016). Volunteer Registry Database forms will be submitted to the National Institute of Health's Office of Regulatory Compliance and Quality at the completion of the research study.

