A baseline ultrasound grayscale scan will be used to identify the tumor and to evaluate the following criteria: size, shape, and orientation of the lesion; echogenicity compared to surrounding tissue. Standard power Doppler of the lesion will also be performed. When possible, previous MR/CT data will be uploaded onto the scanner in order to perform image fusion for ultrasound guidance during imaging. The distribution of color signals and the overall color content of the tumor will be evaluated by comparing the pattern and amount of color to the normal surrounding tissue. Following baseline scanning, patients will receive a 1 ml intravenous injection of Optison (GE Healthcare, Princeton, NJ) in a peripheral vein followed by renal mass imaging in 2D CHI (a nonlinear contrast imaging package). Ten minutes after the 2D CEUS exam, patients will receive a second bolus injection of Optison followed by 3D CHI (using a curvilinear 3D array). All contrast injections will be supervised by a board certified physician. Resuscitation equipment and trained personnel will be immediate proximity to the patient during each contrast-enhanced ultrasound exam. Digital clips of the exams will be recorded through the contrast agent wash-in and wash-out phases for at least two minutes and stored for later use. The subject will then be monitored for adverse reactions for 30 minutes. If the patient wishes to continue participating in the study, they will be eligible for CEUS exams during their future clinically scheduled follow up exams as long as these take place within the study timeframe.

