#### 6.4 Safety Monitoring

Patients will be monitored for AEs during and 30 minutes after contrast administration. All other procedures will be performed according to standard of care. No further patient monitoring is required as side effects of Optison are acute in nature and no renal toxicity has been reported (See Table 1, section 2.1).

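### The AE data-form rule stops at the end of Optison administration, but AE monitoring runs for a further 30 minutes

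*Combined protocol and SAP*

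**What the plan says.** **Recording.** Section 6.6.2 states that all AEs, whether observed or volunteered and whether or not linked to the drug, "occurring from the initiation of Optison dosing until the completion of the Optison administration will be recorded" on a serious or non-serious AE data form. The form's contents include severity, onset date, resolution date and relationship to the drug.

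**Monitoring.** Four other sections describe a longer period:

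- Section 6.4: "Patients will be monitored for AEs during and 30 minutes after contrast administration". It adds that nothing further is needed after that.
- Section 6.6.1: "Adverse events will be monitored during the entire procedure and for 30 minutes post injection".
- Section 6.3, after describing the imaging: "The subject will then be monitored for adverse reactions for 30 minutes".
- Section 3.1: "The entire ultrasound imaging protocol will require approximately one hour including a 30 min observation period".

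Section 6.6 also says "Adverse events will be monitored during the entire procedure", and section 6.6.2 repeats that idea immediately before the recording sentence.

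**Dosing.** There are two injections per exam. Section 6.3 places the second one: "Ten minutes after the 2D CEUS exam, patients will receive a second bolus injection of Optison". Section 6.7 makes both injections a condition of completing the trial.

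**Use of the data.** Section 2 lists a tertiary aim on the safety of Optison in patients with renal impairment. The synopsis does not list this aim, and section 7.2 contains no safety analysis.

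**The concern.** The protocol plans to observe patients for AEs during a period that its form-recording sentence leaves out. The 30-minute observation is the last planned chance to detect a reaction, and apart from the 3D exam it is the only monitored time after the final dose. The reactions described in sections 1.1 and 6.6.1 are mostly mild and transient. They would usually be non-serious, so the separate SAE rule would not pick them up.

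The AE data form is where severity, onset and relationship are captured. Staff who follow the recording sentence to the letter could leave later non-serious events off it, and a form-based AE count for the tertiary safety aim would then be too low. Staff who follow the other AE rules would record them. Two coordinators could therefore handle the same event differently, each with support in the protocol.

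**Working it through.** The plan states no figure to reproduce. The check compares the two windows and adds up minutes.

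**Step 1: what completion of administration means.** Section 5.1, headed Administration, describes a bolus intravenous injection. Section 6.4 places the 30 minutes after contrast administration, and section 6.6.1 separates reactions during administration from those following it. In the protocol's own usage, administration is the injection and is over before the observation begins. With two injections per exam (sections 6.3 and 6.7), it is complete at the end of the second bolus.

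**Step 2: the two windows side by side.**

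| Part of the exam | Monitored for AEs? | Inside the form sentence? |
|---|---|---|
| First bolus and 2D exam | Yes | Yes |
| Ten-minute wait | Yes | Yes |
| Second bolus | Yes | Yes |
| 3D exam | Yes | No |
| Final 30-minute observation | Yes | No |

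**Step 3: monitored time outside the form sentence, per exam.** The sections start the 30 minutes at different points, so there are two counts.

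- From the last injection (sections 6.4 and 6.6.1): 30 minutes.
- After imaging (section 6.3), where clips are "recorded through the contrast agent wash-in and wash-out phases for at least two minutes": at least 2 minutes of 3D clip + 30 minutes of observation = at least 32 minutes.

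For scale, section 3.1 puts the whole visit at about 60 minutes including the 30-minute observation: 30/60, or about half the visit time.

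**Step 4: does any other rule extend the form sentence?**

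| Rule | Location | End time given? | Changes the form window? |
|---|---|---|---|
| AE definition: onset or worsening after medication starts | 6.6.2 | No | No |
| Investigator's assessment of each AE | 6.6.2 | No | No |
| Central reporting of all AEs to the Clinical Trial Support Office | 6.6.2 | No | No |
| Relationship assessment entered on a data form | 6.6.2, Relationship to Optison Administration | No | No, but implies a form for every AE |
| Written report of any SAE during the study | 6.6.2, Serious Adverse Events | Study-wide | No; covers SAEs only |
| Data forms for all enrolled subjects | 7.1 | No | No |
| Final report to the IRB, including all AEs | Appendix A, A | No | No |
| Participant experience recorded on CRFs | Appendix A, C | No | No |

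None of these restates the recording sentence with a later end. They are wider in scope and leave the narrower sentence standing.

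**Step 5: how many AEs could be missed.** This cannot be calculated. Table 1 gives AE frequencies from earlier studies but no onset times, so there is no basis for dividing events into those before and after the second bolus.

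**The case against.** The strongest reply is that this is loose wording which nobody would apply literally. The preceding sentence in section 6.6.2 speaks of monitoring the whole procedure. The form fields as listed are dates, not clock times, so an event before the second bolus and one 20 minutes after it would carry the same onset date. The resolution date looks well beyond the injection. The recording sentence says what is recorded and never says that later events are not. Appendix A requires participant experience to be put on CRFs without any cut-off, and the relationship assessment goes on a data form for any AE. The aim is tertiary and absent from the synopsis, and no safety analysis is planned. On this view the matter is a minor clarification.

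Much of this stands. The untimed rules make actual loss of data less likely and make a drafting slip the most plausible explanation. The consequence is conditional on which sentence staff follow. The Appendix C forms are not reproduced, so their instructions cannot be checked in either direction.

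It does not remove the inconsistency. Taking administration to mean the whole visit conflicts with sections 5.1, 6.4 and 6.6.1. The only sentence that sets a period for completing the AE form ends too early. The absence of clock times also cuts the other way: from the listed fields, nobody could later tell which reading a coordinator had applied.

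**Conclusion.** The inconsistency is real and should be fixed; its weight is minor to moderate. Read literally, the form window ends with the second bolus and omits 30 minutes of planned AE monitoring per exam, or at least 32 minutes if observation starts after the 3D clip. Only non-serious AEs beginning in that interval are exposed, and only on the form.

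This rests on reading administration as the injection, which is how the protocol uses the word elsewhere, and on the appendix forms not already setting a wider window. Confidence is high that the texts disagree. Whether any AE data would be lost depends on site practice and cannot be judged from the documents. SAE reporting, central AE reporting and the accuracy aims are not affected.

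**What to change.** Amend the recording sentence in section 6.6.2 so that the AE data form covers the whole period the protocol already monitors: from the first Optison injection to the end of the 30-minute observation that follows the last injection and its imaging. In the same edit, reconcile the starting point of that observation, since sections 6.4 and 6.6.1 count from the injection and section 6.3 counts from the end of imaging. Check the result against section 3.1 and the relationship and SAE subsections of 6.6.2.

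Put the same window in the CRF instruction, and use it for any AE summary that is produced.

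The cost is a one-sentence amendment and a matching line on the form. No procedure or visit time is added, because the observation already takes place. The recorded AE count may be higher than under the literal rule.
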